The purpose of this pilot study is to observe the effects of up to eight 8-weekly cycles of subcutaneous recombinant interleukin-2 (SC rIL-2) on levels of replication-competent HIV in blood CD4 T cells in 20 participants with chronically suppressed HIV infection (viral load <50 copies/mL) who are stable on the same ART regimen for at least one year and have a CD4 T cell count ≥ 350 cells/mm³. We hypothesize that IL-2 administration will result in a reduction of the replication-competent reservoir, as measured by the QVOA assay, compared to the baseline values in this population.

B.1. STUDY ENDPOINTS AND OUTCOME MEASURES

The primary endpoint of the study is the change in the level of replication-competent virus from baseline to the end of rIL-2 treatment, as measured by the Quantitative Viral Outgrowth Assay (QVOA).

B.2. PRIMARY OBJECTIVE

The primary objective will be to compare levels of replication competent HIV in circulating CD4 T cells before and after up to 8 cycles of rIL-2 administration. The frequency of CD4 T cells containing replication-competent virus in leukapheresis samples obtained at baseline and at the end of rIL-2 treatment will be enumerated using several state of the art methods. The primary readout for this objective will be measurement of replication-competent virus by Quantitative Viral Outgrowth Assay (QVOA) performed by [name]'s group at Accelevir.

B.3. SECONDARY OBJECTIVES

- 1) To examine the relationships between levels of replication competent HIV as identified by QVOA and other measures of HIV persistence:
 - a) the intact proviral DNA assay ([name]),
 - b) the Envelope Detection by Induced Transcription-based Sequencing (EDITS, [name]) performed on the same pre-trial and post-trial leukapheresis samples.
- 2) To explore the effects of rIL-2 administration on induction of HIV expression in vivo as measured by the EDITS assay and plasma HIV levels.
- 3) To examine the effects of rIL-2 administration on natural killer cell phenotype and function and on the ability of NK cells to limit HIV propagation in vitro.

C. METHODS

C.1. STUDY DESIGN

This is an open label pilot study of 20 participants with chronically suppressed HIV infection (viral load <50 copies/mL), stable on an ART regimen for at least one year, who have a CD4 T cell count ≥ 350 cells/mm³. All participants will receive rIL-2.

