All participants will receive rIL-2, 5 million units (MU) subcutaneously (SC) twice a day \times 4 consecutive days, every 8 weeks, for 8 cycles in addition to ART.

Ideally, rIL-2 doses should be 10 – 12 hours apart, but no closer than 6 hours, and no greater than 18 hours apart.

If at any point rIL-2 is discontinued, efforts will be made to maintain follow-up for all data collection as outlined in the schedule of events.

C.2. STATISTICAL CONSIDERATIONS

C.2.1. Analytic Plan

The primary analysis will test whether the change in the size of the replication-competent reservoir, as measured by the modified QVOA assay, from baseline to two weeks after the last rIL-2 infusion is significantly different than is expected by random variation. In this intent-to-treat analysis, all participants who received at least one dose of IL-2 will be included. Secondarily, we will perform an on-treatment analysis including only the subset of participants who received all eight planned IL-2 cycles. We will use mixed effects models to estimate the effect of IL-2 treatment on the replication-competent reservoir among all participants, controlling for possible confounding factors including at a minimum CD4 T cell count at baseline and at pre-ART nadir, duration of virologic suppression, type of antiretroviral regimen at study entry, historical peak plasma HIV RNA, and demographic factors.

We will then fit the relevant models to address the following secondary objectives:

- a. Replicate the analyses above in the on-treatment population, i.e., those who received all 8 planned IL-2 cycles.
- b. In the intent-to-treat population, add a term indicating the number of IL-2 cycles each participant received. This will account for variability of total dose, and the associated parameter and its interaction to time point will provide an estimation of the effect modification expected from repeated dosing. We will assess for non-linearity of any dose effect both graphically and formally, and fit higher-order terms as suggested by those analyses, to explore whether there is a threshold effect (i.e., whether the effect size changes drastically past a given number of doses), an analysis that was not reported in the original Chun paper.

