3. HIV-1 infection, documented by and FDA-approved ELISA, EIA, or rapid antibody detection method, and confirmed by a second approved antibody-based test or by a positive approved HIV RNA detection assay.
4. CD4+ T cell count ≥ 350 cells/mm 3 .
5. HIV-1 RNA < 50 copies/mL obtained within 60 days prior to study entry performed with an FDA-approved HIV-1 RNA assay.
6. Adequate venous access and no other contraindications for leukapheresis.
7. Absolute neutrophil count (ANC) ≥ 1500 /mm 3 .
8. Hemoglobin level >10 g/dL.
9. Platelet count $\geq 100,000$ /mm 3 .

² Accelevir, data on file

10. Serum creatinine ≤ 1.5 mg/dL
11. AST and ALT < 2.5 times the upper limit of normal
12. TSH, T3, and T4 levels within the normal range of the processing laboratory.
13. Anti-thyrosine peroxidase (TPO) antibodies within the normal range of the processing laboratory.
14. Willing to comply with study-mandated evaluations; including not changing antiretroviral regimen (unless medically indicated) during the study period.
15. All participants must have received HAART, and had viral loads below the limit of quantification of the assay for at least 1 year. Participants who had intermittent isolated episodes of detectable low-level viremia < 500 copies RNA/mL flanked by viral loads below the limit of quantification of the assay will remain eligible.
16. On a stable combination antiretroviral regimen (no changes to treatment within 4 weeks of enrollment) including at least 3 medications and willing to continue on current antiretroviral therapy for the duration of the study, unless otherwise medically indicated.

C.4. EXCLUSION CRITERIA

1. Childbearing potential for female participants. For the purposes of this study, a woman is considered to be of childbearing potential if she is not postmenarchial, has not had a documented surgical sterilization procedure, has an intact uterus and at least 1 ovary, and has had a spontaneous menstrual period in the last 2 years.
2. Acute or chronic hepatitis C infection, defined as a positive plasma HCV RNA using any FDA-approved qualitative or quantitative test in a participant with a positive HCV antibody (HCV RNA testing is not required in participants with a negative HCV antibody). Participants who have completed a course of a direct-acting antiviral agent for hepatitis C and have a confirmed plasma HCV RNA level below the limit of detection of the assay 12 weeks or longer after completion of therapy will be eligible.

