- Delivery of pre-filled cycle doses of rIL-2 and review of handling, storage, and administration procedures
- CBC and metabolic panel
- Thyroid function tests and anti-Tpo antibodies
- CD4+ and CD8+ T cell count (both absolute and as percent of lymphocytes)
- Plasma HIV RNA level by PCR (using the locally available assay)
- PBMC will be cryopreserved for assays of immune cell phenotype and NK cell phenotype
- Plasma will be cryopreserved for single copy HIV RNA assay
- The participant will be observed as he/she administers the dose of rIL-2 (approximately 5 million units) subcutaneously.

D.2.6. rIL-2 Treatment Cycles 4 and 8, Day 7

Participant returns to clinic for:

- Interval history and complete physical examination.
- Concomitant medication review
- Tolerance and compliance with injection schedule
- CBC and metabolic panel
- CD4+ and CD8+ T cell count (both absolute and as percent of lymphocytes)
- Plasma HIV RNA level by PCR (using locally available assay)
- PBMC will be cryopreserved for assays of immune cell phenotype and NK cell phenotype
- Plasma will be cryopreserved for single copy HIV RNA assay

D.2.7. rIL-2 Treatment Cycles 2 and 3, Day 0

NOTE: Each treatment cycle should begin 7-10 weeks after start of last treatment cycle. These visits will include:

- Interval history and targeted physical examination, including weight.
- Concomitant medication review.
- Delivery of pre-filled cycle doses of rIL-2 and review of handling, storage, and administration procedures

- CBC and metabolic panel
- Thyroid function tests and anti-Tpo antibodies
- CD4+ and CD8+ T cell count (both absolute and as percent of lymphocytes)
- Plasma HIV RNA level by PCR (using the locally available assay)
- IL-2 immunogenicity (cycle 2 only)

D.2.8. rIL-2 Treatment Cycles 5, 6, and 7, Day 0

NOTE: Each treatment cycle should begin 7-10 weeks after start of last treatment cycle. These visits will include:

- Interval history and targeted physical examination, including weight.
- Concomitant medication review.
- Delivery of pre-filled cycle doses of rIL-2 and review of handling, storage, and administration procedures
- CBC and metabolic panel
- Thyroid function tests and anti-Tpo antibodies
- CD4+ and CD8+ T cell count (both absolute and as percent of lymphocytes)
- Plasma HIV RNA level by PCR (using the locally available assay)

D.2.9. rIL-2 Treatment cycles 1-8, Days 2 and 4

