Staff will contact the participant by phone to assess tolerance and compliance with injection schedule

D.2.10. End of Study Visit (or Premature Discontinuation Visit)

NOTE: The end of study visit should take place 8 weeks (+/- 2 weeks) after Day 0 of the last (8th) treatment cycle. In the case of premature discontinuation, the end of study visit should take place at least 6 weeks after day 0 of the last treatment cycle and may take place up to 10 weeks after day 0 of the last treatment cycle.

These visits will include:

- Interval history and targeted physical examination.
- Immunogenicity testing
- CD4+ and CD8+ T cell count (both absolute and as percent of lymphocytes)
- Plasma HIV RNA level by PCR (using the locally available assay)
- IL-2 immunogenicity
- At this visit the participant will undergo a 4 Liter leukapheresis at the Seidman Ambulatory Stem Cell Transplant Unit at University Hospitals using AIDS protocol 328.
- Plasma will be cryopreserved for single copy HIV RNA assay
- Leukapheresis product PBMC will be cryopreserved for:
 - HIV reservoir assay by EDITS
 - HIV reservoir assay by QVOA
 - Total and intact proviral DNA assay (Accelavir)
 - Assays of immune cell phenotype and NK cell phenotype

If leukapheresis cannot be done after premature treatment discontinuation for any reason, a 120 cc. blood draw will be obtained for preparation of PBMC and plasma. Based upon cell yield these samples will be used for:

- Plasma will be cryopreserved for single copy HIV RNA assay
- HIV reservoir assay by EDITS
- HIV reservoir assay by QVOA
- Total and intact proviral DNA assay (Accelavir)
- Assays of immune cell phenotype and NK cell phenotype

D.2.11. Immunogenicity follow-up

Participants who have detectable neutralizing antibodies at the end of study visit will be followed approximately every 90 days for repeat testing until 12 months after the end of study or until a negative result is obtained. During these visits, an interval medical history and targeted physical exam will be conducted. If clinically significant events have occurred, the participant will be referred for appropriate medical care.

D.2.12. Management of off-window visits

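### The fallback blood draw for the final QVOA is limited to early stoppers, so an eight-cycle completer who cannot have the second leukapheresis has no protocol-provided specimen for the primary endpoint

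*Combined protocol and SAP*

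**What the plan says.** Section B.1 defines the endpoint: "The primary endpoint of the study is the change in the level of replication-competent virus from baseline to the end of rIL-2 treatment", measured by QVOA. Section B.2 names the specimen: "leukapheresis samples obtained at baseline and at the end of rIL-2 treatment will be enumerated".

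Section D.2.10 covers both the end of study visit and the premature discontinuation visit. The rule is "At this visit the participant will undergo a 4 Liter leukapheresis at the Seidman Ambulatory Stem Cell Transplant Unit", with the product stored for QVOA among other assays. The exception reads "If leukapheresis cannot be done after premature treatment discontinuation for any reason, a 120 cc. blood draw will be obtained". Use of that draw is itself conditional: "Based upon cell yield these samples will be used for" the plasma assay, EDITS, QVOA, proviral DNA and phenotyping.

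Fitness for the procedure is an entry criterion in C.3: "Adequate venous access and no other contraindications for leukapheresis".

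For the primary analysis C.2.1 states: "In this intent-to-treat analysis, all participants who received at least one dose of IL-2 will be included". It adds an on-treatment analysis restricted to those who received all eight cycles. It gives no rule for a missing final QVOA.

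**The concern.** The protocol foresees that a second leukapheresis may not be possible, and it accepts a blood draw as a source of cells for QVOA. It then offers that draw only to participants who stopped treatment early and gives no reason for the limit. The uncovered participants received the full course. They make up the whole on-treatment analysis and hold the highest cycle counts in the dose-response model of C.2.1.

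A completer without a final sample can stay in a mixed model through the baseline value, but adds no observed change to the primary analysis and nothing to the on-treatment estimate. In a single-arm pilot of about 20, with one baseline and one final measurement each, that value cannot be recovered from another visit.

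**Working it through.** **1. Does any other rule supply a final QVOA specimen for a completer?**

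| Place | What it provides | Covers a completer without leukapheresis? |
|---|---|---|
| D.2.10, main rule | QVOA from the leukapheresis product | No |
| D.2.10, fallback | 120 cc draw after premature treatment discontinuation | No |
| D.2.4 (cycle 1, day 7) | Cells for EDITS and phenotyping | No QVOA |
| D.2.5 and D.2.6 (cycles 4 and 8) | "PBMC will be cryopreserved for assays of immune cell phenotype and NK cell phenotype" | No QVOA |
| D.2.12 (off-window visits) | Moves a visit by a few days or records it as missed | No other specimen |
| D.4.1 (re-draws) | Administrative or laboratory error only | No |
| F.1 | Lists completion under permanent treatment discontinuation | No: D.2.10 requires it to be premature |

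**2. Time between the two procedures.** Baseline leukapheresis is 4-8 weeks before cycle 1 (D.2.2). Seven intervals of 7-10 weeks follow (D.2.5, D.2.7, D.2.8), and the end visit is 6-10 weeks after day 0 of cycle 8 (D.2.10).
- Shortest: 4 + 7 × 7 + 6 = 59 weeks.
- Longest: 8 + 7 × 10 + 10 = 88 weeks.

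**3. The plan's own power figure.** Inputs from C.2.2: difference 0.64 IUPM, variance 0.41. Assumed, because not stated: two-sided alpha 0.05 and zero correlation between the baseline and final values, so the variance of the change is 2 × 0.41 = 0.82. With the normal approximation, power = Φ(0.64/√(0.82/n) − 1.96).
- n = 16: Φ(2.827 − 1.96) = 80.7%, which matches the synopsis.
- n = 20: Φ(3.161 − 1.96) = 88.5%, which does not match the 80% in C.2.2.

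The synopsis and C.2.2 attach the same power and interval to 16 and 20 participants. That is a separate inconsistency, and the present point does not depend on which is right.

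**4. Cost of each lost participant.** Exact paired t-test, noncentrality √n × (0.64/SD of change).

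| Pairs | SD set so that N = 20 gives 80% (SD 0.969) | SD = √0.82 (zero correlation) |
|---|---|---|
| 20 | 80.0% | 85.0% |
| 19 | 77.7% | 83.0% |
| 18 | 75.2% | 80.7% |
| 17 | 72.5% | 78.1% |

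Either way the cost is 2 to 3 points per participant.

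**5. Shift in exposure.** A.5 reports an estimate of 10-15% thyroid dysfunction in the two large trials. Applied to 20 participants, that is 2-3 early stoppers and 17-18 completers, or 85-90% of the set. After three lost completers the share is 14/17 = 82% to 15/17 = 88%, a shift of about 2 to 3 percentage points. After one loss it is under 1 point.

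**6. What a 120 cc draw holds.** At the entry floor of 350 CD4 cells/mm³: 350 × 120,000 mm³ = 42 million CD4 cells before processing loss. The 0.03 IUPM limit in A.2, for the older assay, corresponds to about 1/0.03 = 33 million cells if one infectious unit in the input is the limit. The input of the modified assay is not stated.

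**The case against.** Several points on the other side stand.

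- **Some obstacles already lead to the draw.** Thromboembolism, platelets below 50,000/mm³, or need for a prohibited medication during treatment are grounds for permanent discontinuation in F.1, and so open the fallback. What remains is mainly loss of venous access, refusal, or a problem arising after the last cycle. The final visit also has a four-week window, so a transient obstacle need not lose the sample.
- **Treated participants have done it once.** The baseline leukapheresis precedes cycle 1, so a high failure rate the second time cannot be presumed.
- **The draw may not yield a QVOA.** Its use depends on cell yield and is shared among assays. A low-input sample only after treatment also gives a different detection limit at the two time points, which could mimic or hide a reduction.
- **Unseen documents.** The Manual of Operations holds the schedule of events, and collection volumes are in a separate laboratory document. Neither was available, and nothing in the protocol forbids an ad hoc draw.

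These limit the consequence and shape the remedy. They do not remove the gap: D.2.10 is the protocol's own rule for this sample, and it leaves completers out.

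A reader might infer that losing at least one completer is likely. Assumed failure rates of 5%, 10% or 15% among 17-18 completers do give 58-60%, 83-85% or 94-95%, from 1 − (1 − p)^n. But no such rate appears in the documents, and 17-18 is an upper figure because it counts thyroid stops only.

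**Conclusion.** The gap is real on the text. A completer who cannot have the second leukapheresis has no protocol-provided specimen for the primary endpoint, contributes no observed change, and is lost to the on-treatment estimate. If 80% power at N = 20 is taken as stated, one, two or three such losses leave 77.7%, 75.2% or 72.5%, assuming a two-sided 0.05 paired t-test. How many will occur cannot be judged from the documents.

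Three stronger readings are not supported.
- **That the primary analysis is materially tilted toward low exposure.** The shift is at most about 3 percentage points for three losses.
- **That power falls from 80% at 16 to about 70%.** The plan treats about 20. If 16 gives 80%, then 19, 18 or 17 remaining pairs give 87%, 85% or 83%.
- **That early stoppers are assured an endpoint.** Their draw also depends on cell yield.

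The point is worth acting on because the correction is nearly free, and the sample cannot be replaced later.

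**What to change.** In D.2.10, delete the four words that restrict the fallback to premature treatment discontinuation, so that the 120 cc draw is taken from any participant at the end of study visit when leukapheresis cannot be done. In the same paragraph, give QVOA priority over the other assays when cells are limited.

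In C.2.1, add three sentences:
- record the cell input of every QVOA;
- treat a negative draw-based result as censored at the detection limit implied by its own input;
- flag draw-based results and repeat the primary analysis without them.

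Check that the Manual of Operations says the same.

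The cost is a four-word deletion, a few added sentences and one sensitivity analysis; the draw is already a protocol procedure. The downside is fewer cells, lower sensitivity after treatment than at baseline, and sometimes no QVOA at all. The change therefore narrows the gap without closing it, and C.2.1 still needs a stated rule for participants whose final QVOA remains missing.

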E.1. MANAGEMENT OF SPECIFIC ADVERSE EVENTS

The Guidelines for Dose Modification, (protocol section C.5.2), apply to all of the scenarios listed in this section.

E.1.1. Serious Infections

All subjects will be monitored for signs or symptoms of a serious or local infection at each visit. All subjects who develop a serious infection while on study will be referred for immediate medical care to a qualified healthcare professional. Participants who develop any of the following infectious events will be required to discontinue study treatment:

- Tuberculosis, pulmonary or extrapulmonary
- Non-tuberculous mycobacterial infection, disseminated or extrapulmonary
- *Pneumocystis jirovecii* pneumonia
- Coccidioidomycosis, disseminated or extrapulmonary
- Cryptococcosis, extrapulmonary
- Cryptosporidiosis or isosporiasis, chronic intestinal (greater than 1 month's duration)
- Cytomegalovirus disease (other than liver, spleen, or lymph nodes) and including retinitis with loss of vision
- Histoplasmosis, disseminated or extrapulmonary
- Kaposi's sarcoma
- Lymphoma, Burkitt's or immunoblastic, regardless of anatomical location
- Lymphoma, primary of brain
- Progressive multifocal leukoencephalopathy
- Toxoplasmosis of brain
- Herpes zoster reactivation involving more than one dermatome or visceral involvement including but not limited to viral pneumonia, encephalitis and hepatitis.
- Any serious infection that is considered life-threatening or requires inpatient treatment. Participants who experience other serious infections not listed above that do not require inpatient treatment and are not considered life-threatening will have study treatment temporarily stopped until the infection is controlled. These subjects may restart study drug once the infection is controlled.

Other infections, including local infections, will also require referral to qualified medical treatment. The study principal investigator, in consultation with the SMC if necessary, will determine if an infection not listed above warrants permanent treatment discontinuation.

E.1.2. Acute Hypersensitivity Reactions

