Participants who develop pain, a skin rash, or other clinical manifestation deemed consistent with an episode of herpes zoster, will be immediately referred for evaluation by a qualified clinician, and will be required to discontinue study treatment until any pharmacologic treatment for varicella-zoster has been completed and the clinical manifestations have resolved in the judgment of the treating physician. Participants who develop recurrence of signs or symptoms or herpes zoster reactivation, and those who develop involvement of more than two dermatomes or have evidence of visceral involvement while on study will be required to discontinue study treatment permanently.

Participants who develop a detectable HBV DNA at any time during the study will be required to discontinue study treatment permanently, and will be referred for specialized medical care as soon as the study team becomes aware of a positive HBV DNA result.

E.1.10. Thrombotic Disease

At each visit, signs and symptoms of venous thrombosis will be sought. Participants who develop deep vein thrombosis or pulmonary embolism will permanently discontinue rIL-2 administration.

E.2. MANAGEMENT OF ADVERSE EVENTS ACCORDING TO SEVERITY

E.2.1. Grade 1 or 2 AEs

Participants who develop a Grade 1 or 2 AE may continue study treatment.

E.2.2. Grade 3 or 4 AEs

If the investigators have compelling evidence that the grade 3 or 4 AE has NOT been caused by the study treatment, dosing may continue without modification. In all other cases, the guidelines for dose adjustment will be applied. Refer to sections E.1 and C.6.2 and to Manual of Operations for dosing modification guidelines.

Participants experiencing Grade 3 or 4 AEs will be followed closely for resolution of the AE to

Grade ≤ 2.

E.3. PREGNANCY

Women of reproductive potential will be excluded from enrollment in the study. In the unlikely event that a participant does become pregnant while on study treatment (e.g., tubal ligation failure), study treatment will be permanently discontinued and the participant will be referred for immediate medical evaluation. Any such participants will be encouraged to remain in the study to be followed on study/off study treatment until study completion and will be followed by telephone contact thereafter to determine the pregnancy outcome. Pregnancy-related outcomes (health of the infant) and any pregnancy-related complications (e.g., fetal loss/abnormalities) will be reported on the CRF.

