NOTE: Pregnant participants will be considered on study until the outcome of the pregnancy has been obtained and reported on the CRF.

E.4. REPORTING OF ADVERSE REACTIONS TO THE RESPONSIBLE IRBs

The investigators will report adverse reactions to the responsible IRB in accordance with respective IRB policies and procedures.

Follow-up information to a reported adverse event will be submitted to the IRB as soon as the relevant information is available. If the results of the investigator's follow-up investigation show that an adverse event that was initially determined not to require reporting to the IRB does, in fact, meet the requirements for reporting, the investigator will report it as soon as possible in accordance with respective IRB policies and procedures.

E.5. SOCIAL HARMS REPORTING

Although the study site makes every effort to protect participant privacy and confidentiality, it is possible that participants' involvement in the study could become known to others, and that social harms may result (i.e., because participants could become known as HIV-infected). For example, participants could be treated unfairly or discriminated against, or could have problems being accepted by their families and/or communities.

Social harms that are judged by the study chairs to be serious or unexpected will be reported to responsible site IRB at least annually or according to their individual requirements. In the event that a participant reports social harm, every effort will be made by study staff to provide appropriate care and counseling to the participant, and/or referral to appropriate resources for the safety of the participant as needed.

F. CRITERIA FOR DISCONTINUATION

F.1. PERMANENT TREATMENT DISCONTINUATION

- Interruption of antiretroviral medications for >4 consecutive weeks
- Occurrence of any of the following opportunistic complications:
 - Tuberculosis, pulmonary or extrapulmonary
 - Non-tuberculous mycobacterial infection, disseminated or extrapulmonary
 - *Pneumocystis jirovecii* pneumonia
 - Coccidioidomycosis, disseminated or extrapulmonary
 - Cryptococcosis, extrapulmonary
 - Cryptosporidiosis or isosporiasis, chronic intestinal (greater than 1 month's duration)
 - Cytomegalovirus disease (other than liver, spleen, or lymph nodes) and including retinitis with loss of vision
 - Histoplasmosis, disseminated or extrapulmonary
 - Kaposi's sarcoma
 - Lymphoma, Burkitt's or immunoblastic, regardless of anatomical location

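### For a first, uncomplicated herpes zoster episode in exactly two dermatomes, the protocol's sections disagree on whether rIL-2 may be restarted

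*Combined protocol and SAP*

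**What the plan says.** Four sections of the combined protocol and SAP set a rule for zoster.

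- **E.1.1 (Serious Infections)** opens its list with "Participants who develop any of the following infectious events will be required to discontinue study treatment". The zoster entry is "Herpes zoster reactivation involving more than one dermatome or visceral involvement", and the last entry is "Any serious infection that is considered life-threatening or requires inpatient treatment". Serious infections that are not listed and are less severe "will have study treatment temporarily stopped until the infection is controlled" and may then restart. For the remaining infections, the principal investigator "will determine if an infection not listed above warrants permanent treatment discontinuation".
- **E.1.9 (Viral Reactivation)** says that a participant with zoster "will be required to discontinue study treatment until any pharmacologic treatment for varicella-zoster has been completed and the clinical manifestations have resolved". It makes the stop permanent for recurrence and for "those who develop involvement of more than two dermatomes or have evidence of visceral involvement while on study will be required to discontinue" study treatment.
- **F.1 (Permanent Treatment Discontinuation)** has an entry headed "Occurrence of any of the following opportunistic complications", then a separate zoster entry set at more than two dermatomes or visceral disease, and an entry for life-threatening or inpatient infection. It also has a catch-all for any reason the investigators consider clinically significant.
- **I.6.1.6 (Risk Mitigation Strategy for Viral Reactivation)** holds treatment for any zoster until it is treated and resolved, and requires a permanent stop for recurrence or multidermatomal involvement. The protocol does not define multidermatomal.

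I.6.1.1 adds a general rule that drug is held for a serious infection until it is under control.

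**The concern.** Section G has the investigators decide in real time whether an adverse event meets the criteria for stopping treatment. With two dermatomes involved, the answer depends on which section they open. One who works from E.1.9 and F.1 could give rIL-2 again, once the rash has cleared, to a participant whom I.6.1.6, and by context E.1.1, would keep off drug. What is at stake is re-exposure of an individual to an immunomodulator after a viral reactivation. There is a smaller consequence for the data, because the number of cycles received determines on-treatment status and when the final reservoir sample is taken.

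**Working it through.** The plan states no figure here, so the check applies each rule to the same case and then counts what depends on the answer.

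**1. Isolate the case.** Take a first episode (removes the recurrence triggers in E.1.9 and I.6.1.6), non-visceral (removes the visceral triggers), and outpatient and not life-threatening (removes the serious-infection entries in E.1.1 and F.1). Only the number of dermatomes is left.

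**2. Apply each rule: is a permanent stop mandatory?**

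| Dermatomes | I.6.1.6 (multidermatomal) | E.1.1 (more than one) | E.1.9 (more than two) | F.1 (more than two) |
|---|---|---|---|---|
| 1 | No | No | No; hold | Not listed |
| 2 | Yes, on plain meaning | Yes, by context | No; hold | Not listed |
| 3 or more | Yes | Yes, by context | Yes | Yes |

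The sections agree at one dermatome and at three or more. They part only at exactly two: 2 > 1 is true, and 2 > 2 is false.

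**3. Is E.1.1's stop permanent?** It does not say so, so this is an inference. Two things support it. E.1.1 reserves the temporary stop for serious infections outside its list. Its list also nearly duplicates F.1: 13 named opportunistic conditions plus the life-threatening or inpatient entry match in substance, so 13 + 1 = 14 of 15 entries. The fifteenth is zoster. Three things count against it. E.1.9 uses the same required-to-discontinue wording for a temporary hold, E.1.3 uses discontinued for a reversible stop, and I.6.1.1 speaks of holding drug. On balance the permanent reading is better, because a temporary one would make tuberculosis or cerebral toxoplasmosis restartable under E.1.1, contrary to F.1.

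**4. Cycles that depend on the choice.** For onset after cycle k of 8, a permanent stop allows 0 more. E.1.9 allows at most 8 - k, and fewer if cycles are cancelled during the hold (D.2.13): k = 1 gives 7, k = 4 gives 4, k = 7 gives 1.

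**5. Effect on the analysis.**
- Primary population (C.2.1): at least one dose. With k of 1 or more the participant is included either way.
- On-treatment set (C.2.1): all eight planned cycles. A permanent stop excludes the participant; a restart leaves inclusion possible.
- Cycle-count term (C.2.1): k under a permanent stop, up to 8 under a restart.
- Final QVOA (D.2.10): 6 to 10 weeks after day 0 of the last cycle received. At the nominal 8-week spacing, a permanent stop brings the sample forward by 8 × (8 - k) weeks compared with completing all cycles: 56 weeks for k = 1, 32 for k = 4, 8 for k = 7. If leukapheresis cannot be done after an early stop, D.2.10 substitutes a 120 cc draw, with assays depending on cell yield, so the result itself may be lost.

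**The case against.** The strongest reply is that the only openly worded clash, permanent against temporary, is I.6.1.6 against E.1.9, and it turns on an undefined word. F.1 merely leaves the case out, and E.1.1's permanence is inferred. All of that is true. But removing the disagreement over restart needs two strained readings together: multidermatomal would have to mean three or more, and E.1.1's list would have to be temporary. Even then E.1.1 and F.1 would still carry different numbers for the same event.

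A second reply is that investigators can always comply. E.1.9 sets a minimum hold and orders no restart, F.1's catch-all permits a stop, and D.2.13 lets cycles be cancelled. This stands in part: a permanent stop breaches none of the four sections. It is discretion, however, and does not make a restart consistent with I.6.1.6. C.5.2 likewise defers to the investigator on what is dose-limiting but sets no dermatome threshold.

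Third, the Manual of Operations guides adverse-event management (H.2) and might settle the matter. It was not available. Contradictory thresholds in the protocol should be corrected there in any case.

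Finally, the zoster-specific section and the permanent-stop list both say more than two, so that may be what was meant. This is fair: the documents do not reveal the intent, and only the sponsor can state it.

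**Conclusion.** The point holds, narrowly. For a first, non-visceral, outpatient, non-life-threatening episode in exactly two dermatomes, the sections differ on whether restart is allowed, and no precedence rule is stated. The conclusion rests on the plain meaning of multidermatomal (two or more) and on the contextual reading of E.1.1. The protocol should be corrected because a mandatory safety threshold is inconsistent and the repair is small. The event is expected to be rare in up to 20 participants, although the documents give no rate.

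A reader might infer more than the documents support:

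- *That the investigator faces opposite orders with no compliant course.* A permanent stop satisfies every section.
- *That participants could be dosed through active zoster.* E.1.9 and I.6.1.6 both hold drug until the episode has resolved, so the issue is re-exposure afterwards.
- *That the primary analysis is undermined, or that it is wholly untouched.* Sample size and membership of the primary population do not change, but one participant's QVOA value, its timing or its availability could.

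**What to change.** The sponsor should state one threshold and use it in E.1.1, E.1.9, F.1 and I.6.1.6. The safer default is *more than one dermatome*: put it in place of more than two in E.1.9 and F.1, and in place of multidermatomal in I.6.1.6. If more than two is intended, change E.1.1 and I.6.1.6 instead.

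Two companion edits are needed. Add *permanently* to the lead-in of E.1.1's list. Amend I.6.1.1 so that its general hold-until-controlled rule excludes the permanent-stop events in E.1.1 and F.1; without this, the first edit would sharpen a separate inconsistency.

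The cost is a few words in up to five sections, with no change to sample size or to who enters the primary population. Under the default, a rare participant with two-dermatome zoster loses the remaining cycles and has the final leukapheresis earlier.
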